##### **6.7.2. Study Day**

If the date of interest occurs on or after the first dose date, study day will be calculated as (date of interest – date of first dose) + 1. If the date of interest occurs prior to the first dose date, study day will be calculated as (date of interest – date of first dose). There is no study day 0.

##### **6.7.3. Change from Baseline**

Change from baseline is calculated as (post-baseline result – baseline result).

Percent change from baseline is calculated as (change from baseline/baseline result \* 100).

If either the baseline or the post-baseline result is missing, the change from baseline and/or percentage change from baseline is set to missing as well.

##### **6.7.4. Visit Windows**

Visit windows were +/- 7 Days for Baseline, Visit 3, Visit 4 and Visit 5; +/- 2 Days for Visit 2 and +/-14 Days for Visit 6.

##### **6.7.5. Multiple Assessments**

When multiple assessments are collected on the same date, the average of those assessments will be used in the analyses.

## **6.8. Handling of Missing Data**

### **6.8.1. Missing Efficacy Endpoints**

The missing efficacy data will be imputed by Last-Observation-Carried-Forward (LOCF) method.

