12.2. Analysis Populations

The 2 analysis populations are defined in the study's Statistical Analysis Plan (SAP) as follows:

- Safety Population: All patients who sign informed consent for the study, complete baseline assessments, and receive at least 1 dose of XADAGO.
- Evaluable Population: All patients in the safety population who complete at least the MDS-UPDRS assessment at the Study Day 60 visit.

The principal analysis of the primary endpoint will be conducted for the evaluable population. Sensitivity analysis of the primary endpoint will be carried out for the safety population. Safety summaries will be provided for the safety population.

Eligible, consented, and enrolled study participants will be analyzed based on concomitant PD medication regimen change at Baseline:

Cohort A – Patients that have switched to XADAGO from a Dopamine Agonist

Cohort B – Patients that have switched to XADAGO from an MAO-B inhibitor

Cohort C – Patients that are MAO-B inhibitor naïve

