12.9. Analysis

12.9.1. Primary Outcome Analysis (Observational Assessments)

The change in MDS-UPDRS, PDQ-39, and MoCA from the Baseline Assessment Visit to the Primary Endpoint (Study Day 60) will be analyzed and described in detail in the SAP.

For the endpoints of CGI-C and PGI-C, the data will be dichotomized to have two categories, with 'very much improved' and 'much improved' into one category and the remaining levels into the other.

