## **6. GENERAL CONSIDERATIONS FOR DATA ANALYSES AND HANDLING**

### **6.1. General Summary Table and Individual Subject Data Listing Considerations**

Summary tables and listings (e.g., post text tables and individual subject data listings are prepared according to ICH Guideline E3) include a “footer” providing explanatory notes which indicate at a minimum:

1. Date of data extraction.
2. Date of output generation.
3. SAS program name, including the path that generates the output.
4. Any other output specific details that require further elaboration.

Post text tables also include reference(s) to the subject data listing(s) that supports the summary data. The data extraction date links the output to the archived database that is locked to ensure replication of the results.

In general, row entries in post text tables are made only if data exists for at least one subject (e.g., a row with all zeros will not appear). The only exception to this rule applies to tables that summarize the study termination status of subjects (e.g., reasons for not completing the study). In this case, zeros will appear for study termination reasons that no subject satisfied. The summary tables clearly indicate the number of subjects to which the data apply and unknown or not performed are distinguished from missing data.

Summary tables for medications and medical conditions are coded according to standard dictionaries (e.g., WHO Drug standard dictionary). Adverse event preferred terms and body/organ systems are coded using the latest MedDRA dictionary. The MedDRA dictionary can be used, as well, in the coding of signs and symptoms, medical history, physical examination abnormalities, and clinical diagnoses.

Supportive individual Subject Data Listings, at a minimum, are sorted and presented by investigational site (center). Listings also include subject number, visit number, and visit date.

Other subject data listings that do not support a specific summary table are included to provide an enumeration of the investigator’s general comments. This listing is also organized by investigator. Sorting is also performed with respect to subject, reference visit number and date, visit relative day, date of the comment, and the text of the comment.

Imputed or derived data will be flagged in the individual subject data listings. Imputed data are not incorporated into any raw or primary datasets. These data are retained in derived analysis datasets.

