### **6.5.2. Safety Population**

The ‘Safety Population’ is defined as all subjects who sign informed consent for the study, complete baseline assessments, and receive at least 1 dose of XADAGO.

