### **6.5.3. ITT Population**

The ITT Population is defined as all subjects who sign informed consent for the study, complete baseline assessments, and receive at least 1 dose of XADAGO. ITT population will be used to analyze all efficacy endpoints except MDS-UPDRS.

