#### **6.5.4. Evaluable Population**

The Evaluable population comprises all subjects in the safety population who complete at least the MDS-UPDRS assessment at the Study Day 60 visit. Evaluable population will be used to analyze MDS-UPDRS endpoint.

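### For PDQ-39 and MoCA at Day 60, the SAP's LOCF rule has only the baseline score to carry; the SAP does not say whether it may, and it omits the protocol's Safety-population sensitivity analysis

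*SAP*

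**What the plan says.** **Missing data.** SAP 6.8.1 is one sentence: "The missing efficacy data will be imputed by Last-Observation-Carried-Forward (LOCF) method". Protocol 12.4 says LOCF will usually be used for missing visits. Neither says whether a baseline value may be carried. SAP 6.7.3 says that when the baseline or post-baseline result is missing, "the change from baseline and/or percentage change from baseline is set to missing as well". The order of these two rules is not stated. The nearest hint is SAP 6.1: "Imputed data are not incorporated into any raw or primary datasets. These data are retained in derived analysis datasets".

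**Schedule.** In Protocol Table 3 and SAP Table 2, PDQ-39 and MoCA appear at Visit 1 and next at Visit 3 (Day 60). The Day-30 contact has TSQM-9 as its only scale.

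**Populations.** SAP 6.5.3: "ITT population will be used to analyze all efficacy endpoints except MDS-UPDRS". ITT has the same definition as the Safety Population: "all subjects who sign informed consent for the study, complete baseline assessments, and receive at least 1 dose of XADAGO". SAP 6.5.4, where membership requires a Day-60 MDS-UPDRS, adds: "Evaluable population will be used to analyze MDS-UPDRS endpoint". Protocol 12.2 reads differently: "The principal analysis of the primary endpoint will be conducted for the evaluable population", with the Safety Population as the sensitivity set. Protocol 12.9.1 places under the primary outcome analysis "The change in MDS-UPDRS, PDQ-39, and MoCA from the Baseline Assessment Visit to the Primary Endpoint".

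**Analysis.** SAP 8.4 summarises the changes by cohort and overall and applies a paired t-test. SAP 6.4 reports the number with data, mean, SD, median and range.

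**The concern.** A patient who completes baseline, takes one dose and has no Day-60 PDQ-39 or MoCA is in the ITT set, with only baseline available to carry. If LOCF runs before change is derived, the patient contributes zero; if LOCF is limited to post-baseline values, the patient contributes nothing. Two programmers following the same SAP could therefore report different N, mean and SD.

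This matters because the study has no control arm, and the size of the Day-60 change is its main product. Results are also shown by cohort, so unequal missingness would make equal changes look different. The treatment is known and interim results are to be produced periodically, so a rule left open may be settled by people who have seen data.

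The population mismatch adds to this. The Safety-population analysis of MDS-UPDRS, which would show the effect of restricting to patients assessed at Day 60, is in the protocol but not in the SAP.

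**Working it through.** The documents give no missing rate, effect size, SD or power, so there is no planned figure to reproduce.

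**Step 1: which values can be carried to Day 60?**

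| Scale | Scheduled before Day 60 | What LOCF can carry in the SAP's Day-60 analysis |
|---|---|---|
| PDQ-39, MoCA | Baseline only | Baseline, if allowed |
| CGI-C, PGI-C | None | Nothing |
| TSQM-9 | Day 30 | The Day-30 score |
| MDS-UPDRS | Baseline only | Not needed: the Evaluable Population requires a Day-60 score |

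SAP 6.7.3 defines change as post-baseline minus baseline, so a carried baseline gives exactly 0. An unscheduled or out-of-window earlier score could give another value; the SAP does not say how such a score is treated.

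**Step 2: effect on the reported figures.** Let m be the missing share and d the mean improvement in assessed patients, in units of their SD. With a share m set to zero:

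- N is unchanged, against N(1 − m) for observed cases
- mean = (1 − m)d
- SD = √[(1 − m) + m(1 − m)d²]
- t relative to observed cases = 1/√(1 + md²)

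Assumptions: N = 540, the planned maximum, used as an illustrative ITT size; d = 0.3; m = 5%, 10% or 20%.

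| m | N, observed / carried | Mean, observed / carried | SD carried | t ratio |
|---|---|---|---|---|
| 5% | 513 / 540 | 0.30 / 0.285 | 0.977 | 0.998 |
| 10% | 486 / 540 | 0.30 / 0.27 | 0.953 | 0.996 |
| 20% | 432 / 540 | 0.30 / 0.24 | 0.902 | 0.991 |

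Example at m = 20%: SD = √(0.80 + 0.16 × 0.09) = √0.8144 = 0.902. The 95% half-width is 1.96 × 0.902/√540 = 0.076, against 1.96/√432 = 0.094 for observed cases.

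Over d = 0.1 to 0.5, the SD at m = 20% runs from 0.895 to 0.917. The lowest t ratio over all these values of m and d is 1/√(1 + 0.20 × 0.25) = 0.976. In simulation (20,000 runs), type I error with carried baseline was 0.050 at m = 10% and 0.048 at m = 20%.

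**Step 3: which reading is closer to the truth?** At m = 20% and d = 0.3, truth = 0.8 × 0.3 + 0.2 × (mean change in missing patients).

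| Missing patients | Truth | Carried baseline (bias) | Observed cases (bias) |
|---|---|---|---|
| Changed like the others | 0.30 | 0.24 (−0.06) | 0.30 (0) |
| Did not change | 0.24 | 0.24 (0) | 0.30 (+0.06) |
| Worsened by 0.3 SD | 0.18 | 0.24 (+0.06) | 0.30 (+0.12) |

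**Step 4: does imputation from baseline help?** This is a large-sample check with 20% missing, higher baseline more often missing (logit slope 0.7) and an assumed baseline–improvement correlation of −0.3. Regression imputation stands in for multiple imputation.

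- Missingness depends on baseline only: truth 0.295, observed cases 0.333, carried baseline 0.267, imputation 0.294.
- Missing patients are also 0.3 SD worse than predicted: truth 0.240, plain imputation 0.298, imputation shifted by −0.3 SD 0.238.
- Correlation sign reversed, missingness on baseline only: truth 0.30, observed cases 0.26, carried baseline 0.21. The direction of the observed-case bias therefore depends on an assumption; imputation still recovers the truth.

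**The case against.** **LOCF usually means post-baseline values only.** On that reading nothing is carried and 6.7.3 applies. This is a fair reading, but the SAP does not state it. It would leave TSQM-9 as the only scale on which LOCF can act in the SAP's Day-60 analysis, so a programmer could infer that baseline was meant to be carried.

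**A contradiction?** A reader might infer that 6.8.1 and 6.7.3 conflict, or that the SAP prescribes baseline carried forward. Neither is supported: stating an order reconciles them, and SAP 6.1 only hints at one.

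**Little is missing and the test is unaffected.** Protocol 10.1.4 lets patients who stop XADAGO stay and be assessed, so the missing share may be small. However, Protocol 12.4 says missing PRO items are generally not imputed, so a patient who attends Day 60 may still lack a PDQ-39 score. The t-test point stands: the documents do not support a claim of a false significant result.

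**The 540.** Protocol 8.2 and SAP 4.3.1 call these patients evaluable, while the protocol synopsis says only enrolled. If evaluable has its defined meaning, all 540 have a Day-60 MDS-UPDRS. The counts above are illustrative; the ratios do not depend on them.

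**Populations.** A reader might infer that Protocol 12.2 requires the Evaluable Population for PDQ-39 and MoCA. That goes too far: Protocol 12.2 does not name the scales in its primary endpoint, Protocol 7.2 lists all six instruments at Day 60, and Protocol 12.9.1 also covers CGI-C and PGI-C. Evaluable is defined by MDS-UPDRS alone, so it would discard observed PDQ-39 and MoCA scores and still admit patients who lack them. What stands is narrower: MDS-UPDRS is a primary endpoint on any of these readings, and its Safety-population analysis is absent from the SAP.

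**Conclusion.** The point holds and should be fixed before database lock. The existence of the gap is certain from the text; its size is not. If baseline is carried, the mean is multiplied by (1 − m), and the SD and interval shrink. At an assumed 20% missing, the mean is multiplied by 0.80, the SD is about 0.90 of the observed-case value, and the half-width is 0.076 against 0.094 SD. At 5% missing the mean falls by only 5%. The paired t statistic keeps at least 97.6% of its value over the range examined. Zero change assumes no unscheduled earlier score.

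It would be wrong to conclude that observed cases are unbiased: if missing patients did worse, they overstate improvement more than carried baseline does. That is why a stated rule needs a sensitivity analysis beside it. The missing Safety-population analysis of MDS-UPDRS is a separate departure from Protocol 12.2, and the same carry-forward question would arise there.

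**What to change.** 1. **SAP 6.8.1.** State that baseline is not carried forward to Day 60 and that 6.7.3 governs change scores. Report N, mean and SD for patients with observed Day-60 scores. Say how unscheduled or out-of-window scores are treated. If a zero-change analysis is shown, label it as baseline carried forward.
2. **Sensitivity analysis.** In the ITT/Safety set, use multiple imputation from baseline data for PDQ-39, MoCA and MDS-UPDRS, with a range of fixed worse-outcome shifts for missing patients. This restores the Safety-population analysis of Protocol 12.2.
3. **Populations.** Reconcile SAP 6.5.3 and 6.5.4 with Protocol 12.2 and 12.9.1, and say which scales form the primary endpoint. Do not drop observed Day-60 PDQ-39 or MoCA scores because MDS-UPDRS is missing.

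The cost is SAP wording and several extra programmed tables (three scales, by cohort and overall, with shift scenarios). No new data are needed. The reported N for PDQ-39 and MoCA will be smaller than the ITT N wherever Day-60 scores are missing.

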- Baseline Assessment Visit at the PI's clinic, including electronic completion of ClinRO measures by the PI/certified HCP designee and PRO measures by the patient (by use of a smartphone, tablet, or desktop, based on site and patient electronic capabilities) (Study Day 1)
- Telephone follow-up with the patient by the PI/certified HCP designee (Study Day 30)
- Primary Endpoint Assessment Study Visit at the PI's clinic including electronic completion of ClinROs by the PI/ certified HCP designee and PROs by the patient (Study Day 60)

Eligible patients who compliantly complete the Main Study may participate in the 4-month Extension Study ([Table 3:Schedule of Assessments](#)), which will include:

- Two follow-up Study Visits at the PI's clinic, including electronic completion of ClinROs by the PI/certified HCP designee and PROs by the patient (Study Days 90 and 180)
- One scheduled PRO assessment to be completed electronically by the patient on Study Day 120

If an enrolled patient discontinues XADAGO treatment for any reason at any point in the study (i.e., prior to Study Day 60 for the Main Study or Study Day 180 for the Extension Study), the patient is permitted to remain on study and complete the full schedule of assessments per protocol, as long as the patient is otherwise eligible and is able and willing to continue participation and complete the Main Study (through Study Day 60) or the Extension Study (through Study Day 180).

Number of Patients (planned):

Up to 540 patients enrolled

Inclusion Criteria:

1. Patient (and Care Partner, if required per Inclusion Criterion 7) is able to understand and provide signed informed consent and HIPAA authorization in English
2. Patient with diagnosis of idiopathic PD (all stages)
3. Male or female, 30 to 80 years of age, inclusive, at initial screening assessment
4. Independent of the study, clinician's and patient's choice of treatment is XADAGO in accordance with the Package Insert indication ([Appendix A](#))
5. Patient is willing and able to participate in the study and complete study-related assessments for 2 months and, if eligible, continue for a 4-month study extension
6. Patient has access to an electronic device for the interim completion of PROs

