7. Patient has an available Care Partner who is able and willing to assist with clinic attendance and completion of study assessments (e.g., PROs, health outcomes, etc.), if in the PI's opinion, assistance is needed to comply with all study visits and procedures

Exclusion Criteria:

1. Any of the warnings, precautions, or contraindications listed in the Package Insert ([Appendix A](#)) that in the opinion of the PI would prevent appropriate treatment with XADAGO or impair study participation (e.g., pregnancy, lactation, severe hepatic impairment, etc.)
2. Participation in any other clinical trial of an investigational drug or device within 4 weeks prior to the Baseline Visit or at any time during the study
3. Patient is currently receiving chemotherapy or radiation for any form of cancer (if history of cancer, must be in clinical remission at study entry) or currently receiving immunotherapy
4. Patients with conditions that are likely to prevent them from accurately and reliably completing study assessments, including evidence of moderate or severe dementia as determined by the clinician (not to include mild cognitive impairment [MCI]); major psychiatric illness (specifically diagnosis of schizophrenia, bipolar disorder or a history of attempted suicide); and/or severe and progressive medical illness (including terminal cancer, end-stage renal disease +/- undergoing dialysis)
5. Severe or unpredictable dyskinesia at the time of the Baseline Visit
6. Previous participation in this study; a patient may not re-enroll after prior discontinuation or completion

Medicinal Product, Dosage and Mode of Administration:

XADAGO (safinamide) tablets, 50 mg and 100 mg, oral.

Duration of Patient Participation:

Planned patient participation will be 2 months for patients in the Main Study, including Baseline Assessment and Primary Endpoint Visits at the PI's clinic, and a telephone Follow-up Visit. A window of ± 7 days is allowed for the Baseline Assessment Visit.

Eligible patients participating in the Extension Study (if applicable) will be in the study for a total of 6 months. A window of ± 14 days is allowed for the Clinic Visit on Study Day 180.

Criteria for Evaluation:

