9. SELECTION AND WITHDRAWAL OF PATIENTS

9.1. Inclusion Criteria

1. Patient (and Care Partner if required per Inclusion 7) is able to understand and provide signed informed consent and HIPAA authorization in English
2. Diagnosis of idiopathic PD (all stages)
3. Male or female, 30 to 80 years of age, inclusive, at initial screening assessment
4. Independent of the study, clinician's and patient's choice of treatment is XADAGO in accordance with the Package Insert indication ([Appendix A](#))
5. Patient is willing and able to participate in the study and complete study-related assessments for 2 months and, patients can continue for an optional 4-month study extension
6. Patient has access to an electronic device for the interim completion of PROs
7. Patient has an available Care Partner who is able and willing to assist with clinic attendance and completion of study assessments (e.g., PROs, health outcomes, etc.), if in the PI's opinion, assistance is needed to comply with all study visits and procedures

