12. STATISTICAL METHODS

12.1. General Statistical Considerations

All assessments will be summarized at specified time points. Continuous variables will be summarized using the number of patients, mean, standard deviation (SD), and minimum, median, and maximum values. Categorical variables will be summarized using the number and percentage. All data will be summarized according to cohort and overall.

Endpoints are defined at Study Day 60 (primary endpoint). Descriptive statistics will be provided for all data collected. All tests of significance, unless otherwise stated, will be performed using a two-sided alpha at 0.05.

All analyses will be performed using SAS[®] Version 9.3 or higher (SAS Institute, Inc., Cary, North Carolina, USA).

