12.4. Handling of Missing Values

PROs will handle missing values per the recommended process for that instrument. In general, missing item values for PRO instruments will not be imputed. Missing values will usually result in non-computational item scores for the patient.

Missing visit information will usually be handled by analyzing using last-observation-carried-forward (LOCF) imputations.

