### **5.2. Final Analyses**

After the last enrolled subject completes Visit 3, the database will be locked. The final analyses will be performed after the database lock.

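### SAP 6.8.1 does not limit LOCF by visit, so any Day 90, 120 or 180 summary could, read literally, be filled with earlier scores from patients who never entered the optional Extension or whose visit was not yet due

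*SAP*

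**What the plan says.** The SAP's whole rule for missing efficacy data is one sentence in 6.8.1: "The missing efficacy data will be imputed by Last-Observation-Carried-Forward (LOCF) method". Protocol 12.4 is softer but covers whole visits: "Missing visit information will usually be handled by analyzing using last-observation-carried-forward (LOCF) imputations". Neither text mentions the Extension, a last visit to which the rule applies, or visits not yet due.

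Participation after Day 60 is by choice. Protocol 9.1 says that "patients can continue for an optional 4-month study extension". The synopsis adds a condition, "Eligible patients who compliantly complete the Main Study may participate in the 4-month Extension Study", and otherwise ends follow-up early: "Planned patient participation will be 2 months for patients in the Main Study". The ITT and Evaluable populations (SAP 6.5.3 and 6.5.4) do not require Extension entry.

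On timing, SAP 5.2 has a single lock: "After the last enrolled subject completes Visit 3, the database will be locked". It continues: "The final analyses will be performed after the database lock". No later lock is described. Interim outputs are also planned (Protocol 12.6, SAP 5.1).

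On what is summarised, SAP 8.4 names only the change from baseline to Day 60. Protocol 12.1 is wider: "All assessments will be summarized at specified time points", with descriptive statistics for all collected data. The schedule puts MDS-UPDRS, PDQ-39, TSQM-9, CGI-C and PGI-C at Days 90 and 180, MoCA at Day 180 only, and TSQM-9 alone at Day 120.

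**The concern.** LOCF is meant for a value that should have been observed and was not. A patient who stops at Day 60 as planned has no Day 180 value to miss. An Extension patient at Day 100 when the database locks has not reached Day 180. The SAP separates neither case from true missingness in 6.8.1, and its analysis populations keep both kinds of patient in the denominator.

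A programmer who applies 6.8.1 literally to the summaries promised in Protocol 12.1 would therefore show a Day 180 n near the full population. Much of that n would be scores from an earlier visit. A copied score shows no change since the visit it came from, so an earlier improvement or worsening would look maintained whatever happened to the patients actually followed. Persistence of effect is the main thing an Extension can show, and these summaries may reach posters and publications.

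**Working it through.** **Inputs from the documents.** Planned sample: up to 540 patients from up to 600 screened (SAP 4.3.1; 540/600 = 0.90). It is set by clinical judgment, so there is no power figure to reproduce. Lock: when the last enrolled patient completes Visit 3. Planned calendar: November 2017 to April 2020, with Amendment 2 dated 12 October 2018. The Extension entry rate is not given.

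**Step 1. Simple illustration.** Let e be the share of patients with a real Day 180 value.

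- Share copied = 1 − e. For e = 0.30, 0.50, 0.70 this is 70%, 50%, 30%.
- At e = 0.50, a table with n = 540 rests on 0.50 × 540 = 270 observed values.
- If every copy were a Day 60 score, copies would add zero to the Day 60 to Day 180 change. The tabulated mean change would then be e times that in the observed patients: 30%, 50% or 70% of it.

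**Step 2. Adding the lock.** Let p be the Extension entry rate and A the accrual length in days. Assume uniform accrual and no other dropout. A patient enrolled x days before the last one is at Day 60 + x at lock, so Day d is not yet due for a fraction (d − 60)/A.

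Copied share at Day d = 1 − p × [1 − (d − 60)/A]

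Two values of A bracket the planned calendar:

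- 1 November 2017 to 30 April 2020 is 911 days. If the last completion is a Visit 3, A = 911 − 60 = 851.
- 12 October 2018 to 30 April 2020 is 566 days. If only accrual after Amendment 2 counts and the last completion is a Visit 6, A = 566 − 180 = 386.

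Not yet due at Day 180: 120/851 = 14.1% or 120/386 = 31.1%.

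| p (assumed) | Copied at Day 90, A = 851 | Copied at Day 180, A = 851 | Observed n of 540 at Day 180, A = 851 | Copied at Day 180, A = 386 |
|---|---|---|---|---|
| 30% | 71.1% | 74.2% | 139 | 79.3% |
| 50% | 51.8% | 57.1% | 232 | 65.5% |
| 70% | 32.5% | 39.9% | 325 | 51.8% |
| 90% | 13.2% | 22.7% | 417 | 38.0% |
| 100% | 3.5% | 14.1% | 464 | 31.1% |

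Example: p = 0.70, A = 851 gives 1 − 0.70 × (1 − 0.141) = 0.399.

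**Step 3. Which score is carried to Day 180.** For scales collected at Day 90:

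- Day 60 carried: (1 − p) + p × 30/A
- Day 90 carried: p × 90/A

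At p = 0.70, A = 851 these are 32.5% and 7.4%. At p = 0.90, A = 386 they are 17.0% and 21.0%, so Day 90 copies can outnumber Day 60 copies. For TSQM-9 some patients would carry Day 120 instead. MoCA has no visit between Day 60 and Day 180. An ITT patient without a Day 60 score would carry an earlier one where the scale has one.

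**Step 4. Reach.** Day 60 is earlier than every visit considered here, so none of this changes a Day 60 value.

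**The case against.** The best case for the plan is that the rule already has a scope. Section 6.8.1 is headed as dealing with endpoints, and SAP 3.2, Protocol 7.2 and Protocol 12.1 tie endpoints to Day 60. SAP 8.4 specifies no later efficacy table. Protocol 12.1 speaks of collected data, which a carried-forward score is not. A visit that was never scheduled is arguably not missing at all, and Protocol 12.4 says only that LOCF is usual. Other SAP text points towards observed data: 6.1 separates results not performed from missing ones, 6.4 defines n as subjects with available data, 6.7.3 sets change to missing when either result is missing, and 7.1 reports discontinuation before Day 180.

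This makes a narrower reading possible, and it may be what the authors intended. It does not make that reading explicit. Protocol 12.4 concerns missing visits generally. SAP 6.1 and 6.7.3 do not say whether they act before or after LOCF. The flag for imputed values in SAP 6.1 applies to listings, not summary tables. SAP 6.4 also bases percentages on all subjects in the XADAGO group, which pulls towards full denominators. A disposition table does not change what an efficacy table contains.

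Two criticisms of size stand. A reader might infer that every copied value is a Day 60 score; Step 3 shows otherwise, so the dilution factor e in Step 1 is exact only in that special case. A reader might also infer that standard errors or tests at Day 180 would be too favourable. The planned summaries list n, mean, SD, median, minimum and maximum, without a standard error, and the paired t-test in SAP 8.4 is attached to endpoints defined at Day 60.

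**Conclusion.** The gap is real and should be closed, but it concerns secondary, descriptive output. As written, LOCF has no stated limit by visit or study part, and Protocol 12.1 promises summaries at visits that many patients will not have. Under a literal reading those summaries would overstate n and make earlier changes look maintained.

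It would go too far to say that the primary result is compromised, because the Day 60 analysis is not affected by this mechanism. Nor do the documents show that copied values will certainly appear after Day 60: SAP 8.4 names no such analysis, and the exposure comes from general protocol text.

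The size is unknown because no Extension entry rate is given. Under the assumed entry rates of 30% to 100% and uniform accrual, copies at Day 180 range from 14.1% (everyone enters, 851-day accrual) to 79.3% (30% enter, 386-day accrual). Even full entry leaves some, because the lock comes before the last patients' Day 180 visits.

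**What to change.** Amend SAP 6.8.1 along these lines:

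*LOCF is not applied to visits after Day 60. Day 90, Day 120 (TSQM-9 only) and Day 180 data are summarised as observed cases in patients who entered the Extension and had reached the visit by the data cut-off. Each summary gives n per visit and shows the same patients' baseline and Day 60 values where the scale was collected at those times.*

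The last clause matters because TSQM-9, CGI-C and PGI-C have no baseline assessment. Showing the same patients at each time keeps a change in who is followed from being read as a change in outcome.

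SAP 5.2 should also state the data cut-off or lock that applies to Extension data, and the same rule should govern interim outputs.

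The cost is a few sentences and a smaller n at Days 90 to 180. At 50% entry and 851-day accrual, for example, Day 180 would show about 232 patients rather than 540. No new data are needed and the Day 60 analysis does not change.
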